1.0 Study Summary

Study Title	Prism Adaptation in Left Brain Stroke Rehabilitation
Study Design	Multiple baseline, delayed treatment approach
Primary Objective	To demonstrate the feasibility of adapted methods for assessing and treating spatial and motor function and pain in patients with aphasia and memory impairment.
Secondary Objective(s)	To demonstrate the feasibility of using information about lesion location from the radiology report to classify frontal vs. nonfrontal lesions
Research Intervention(s)/Interactions	Prism Adaptation Treatment (PAT) for spatial neglect in patients with aphasia and memory impairment
Study Population	Left brain stroke patients with aphasia and memory impairment
Sample Size	30
Study Duration for individual participants	7 weeks
Study Specific Abbreviations/ Definitions	DVPRS: Defense and Veterans Pain Rating Scale KF-NAP: Kessler Foundation- Neglect Assessment Protocol PAT: Prism Adaptation Treatment WMFT: Wolf Motor Function Test
Funding Source (if any)	Department of Veterans Affairs

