2.0 Objectives

2.1 Specific Aim 1: To demonstrate the feasibility of adapted PAT procedures in patients with aphasia and memory impairment. Hypothesis: Adapted methods for PAT administration in patients with aphasia are feasible. Even in the presence of memory disorder detecting a treatment signal is possible.

Specific Aim 2: To demonstrate the feasibility of adapted methods for assessing spatial and motor function and pain in patients with aphasia and memory impairment. Hypothesis: Adapted methods for assessing spatial and motor function and pain in patients with aphasia and memory impairment are feasible.

Specific Aim 3: To demonstrate the feasibility of using information about lesion location from the radiology report to classify frontal vs. nonfrontal lesions. Hypothesis: Lesion classification results from radiology reports and brain mapping methods are consistent, confirming this adaptation provides a clinically

accessible, reliable way to identify brain-based predictors of optimal PAT response in future studies.

2.2 Specific Aim 1: Adapted methods for PAT administration in patients with aphasia are feasible. Even in the presence of memory disorder detecting a treatment signal is possible.

Specific Aim 2: Adapted methods for assessing spatial and motor function and pain in patients with aphasia and memory impairment are feasible.

Specific Aim 3: Lesion classification results from radiology reports and brain mapping methods are consistent, confirming this adaptation provides a clinically accessible, reliable way to identify brain-based predictors of optimal PAT response in future studies.

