In addition, brain physiology and anatomy may also define patient subgroups with better response to specific rehabilitation methods (e.g. non-invasive brain stimulation; Plow et al., 2016; Nouri & Cramer, 2011). Although patients across a range of brain lesion locations may experience treatment benefit from PAT (see Yang et al., 2013 for a review), we and others reported that the presence of frontal lobe cortical lesions predicts optimal response to treatment, and subsequent recovery of functional performance in stroke-induced spatial neglect (Chen et al., 2014; Goedert et al., 2018; Gutierrez-Herrera et al., 2018). These experiments were carried out exclusively in right brain stroke-- no data about brain-behavior relationships in recovery from neglect after left brain stroke, with or without treatment, is available. To develop PAT in future large-scale studies as a multi-target treatment for use in patients with both left brain stroke and right brain stroke, first requires determining whether stratifying patients by frontal lobe lesions reveals differences in treatment benefit. The presence of large differences in PAT response related to lesion location would affect the design and evaluation of PAT for stroke rehabilitation as well as eventual clinical decision-making for assigning PAT to eligible stroke survivors. However, clinicians in rehabilitation settings typically obtain information about lesion location from a patient's medical record. Before guidelines for PAT patient selection can be broadly implemented, we must establish that obtaining information about lesion location from the radiology report, as compared to research-based brain mapping methods, is a feasible and reliable method of categorizing lesions.

3.2 Preliminary Study 1: Members of our team have demonstrated that administration of PAT using standardized methods is feasible and yields therapeutic benefits in right brain stroke (Barrett et al. 2012). Purpose: Expert clinicians who assess and treat invisible disabilities like spatial neglect use a variety of rehabilitation techniques (Chen et al. 2017) depending on barriers present, recovery stage, and characteristics of the deficit. However, clinicians carrying out routine care find a large number of choices for spatial neglect

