Preliminary Study 4: Using brain mapping methods, members of our team have shown that right brain stroke patients with frontal lesions respond optimally to PAT (Chen et al., 2014; Goedert et al., 2018). Purpose: Research with neurologically unimpaired individuals suggests that prism adaptation may stimulate lateralized motor-related spatial systems (Fortis, Goedert, and Barrett 2011) linked to frontal cortical brain networks (Ghacibeh et al. 2007). Thus, the presence or absence of frontal brain lesions may affect PAT response. Methods: We had trained raters categorize patients based on their clinical brain images: as having, or not having, a frontal cortical brain lesion (Chen et al. 2014; Goedert et al. 2018). Results: In both studies, patients with frontal brain lesions experienced a more robust therapeutic response to PAT, based on functional performance testing. Although in the first study, medial temporal structures also appeared to play a role in PAT response, this was not confirmed in the second study. Conclusions: A frontal cortical lesion predicts optimal PAT response after right stroke. However, clinical decision-making based on brain mapping with trained raters is not feasible in the clinical environment. This study will extend this work by determining whether obtaining information about lesion location from the medical record is a feasible, reliable way to identify patients with frontal vs. nonfrontal lesions (Aim 3).

3.3 This study is the first to systematically investigate the feasibility of using adapted PAT treatment procedures and spatial-motor-sensory assessments in left-brain stroke patients with aphasia and memory impairment, as well as clinically-accessible methods for identifying patients with optimal response to PAT. This line of research lays the foundation for a potential paradigm shift in the focus of rehabilitation research to PAT as a multi-target treatment to improve spatial function, adaptive movements, functional independence, and pain-free somatic experience. In addition, this study could change the conventional

structure of stroke rehabilitation trials, most of which have not measured the impact of cognitive treatments on motor function, or vice versa, and do not assess the concurrent effect of either cognitive or motor treatment on pain.

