4.0 Study Endpoints *

4.1 We will assess four key aspects of feasibility of our adapted assessment and treatment procedures: acceptability, implementation, adaptation, and limited efficacy testing (Bowen et al., 2009). See Table 1. Acceptability: We will use the Client Satisfaction Questionnaire (CSQ-8; Attkinson & Zwick, 1982; Larsen et al., 1979) to assess satisfaction and perceived value of PAT. We will use the Credibility/Expectancy Questionnaire (CEQ; Devilly & Borkovec, 2000) to assess the degree to which PAT is believable, convincing and logical (credibility) and the expectations for PAT-induced improvement (expectancy). The CSQ-8 and CEQ have been used in patients with subjective cognitive impairment (Foster et al., 2018). Implementation: We will record attendance and completion rates to determine whether KF-NAP®, WMFT and PAT can be carried out as planned. Adaptation: Each session, study staff will complete checklists from the KF-NAP®, the WMFT, and the KF-PAT™ manual (Chen, 2015) to track assessment and treatment fidelity. Notations will be made when modifications to administration methods are required. For the brain mapping, trained raters will map brain lesions using the method from Preliminary Study 4. Then, a blinded neurologist will classify participants as having “frontal” or “nonfrontal” lesions. Using radiology reports, lesions will be classified as “frontal” based on use of that word or “anterior” “premotor” “prefrontal” or “precentral” or as “nonfrontal” if none of those words are present. Limited Efficacy Testing: To detect the acquisition and maintenance of a treatment signal, we will assess spatial-motor-sensory and functional recovery over 7 weeks (Figure 2). We will assess: 1) Functional disability, measured by activities of daily living using the Barthel Index (Mahoney & Barthel 1965) and cognitive and motor function with the FIM or FONE-FIM; 2) Spatial neglect, measured by the Behavioural Inattention Test-conventional subtest (Wilson et al., 1987) and CBS via the KF-NAP® (Chen et al. 2012); 3) Motor function, measured by the WMFT (Lin et al., 2009); and 4) Pain, measured by the Defense and Veterans Pain Rating Scale (Polomano et al. 2016), which includes numbers along with pictures and colors to facilitate nonverbal rating of pain. Assessments will be administered by a trained examiner.

TABLE 1. Study Endpoints.

Key Area	Aim	Question	Analysis on Outcome of Interest

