Acceptability	1	
• Do left brain stroke patients view PAT as a satisfactory and credible tool for rehabilitation?	
• Range of post-PAT satisfaction ratings on CSQ-8• Range of credibility and expectancy ratings on CEQ (pre and post PAT)
Implementation	1,2	
• Can KF-NAP®, WMFT, DVPRS and PAT be implemented as planned in left brain stroke patients?	
• Completion rate for KF-NAP®, WMFT, DVPRS and full 10-session PAT
Adaptation	1,2,3	
• What modifications are necessary for implementation of KF-NAP®, WMFT and PAT in left brain stroke patients?• Is classification of lesion location from the medical record consistent with classification using brain mapping?	
• Number and type of modifications to KF-NAP®, WMFT and PAT protocol• Percent agreement on presence or absence of frontal lesion between radiology report and brain mapping
Limited Efficacy Testing	1,2	
• Is there promise for application of PAT in left brain stroke patients?	
• Visual inspection of recovery trajectories on spatial-motor-sensory and functional assessments over 7 weeks to detect the acquisition and maintenance of a treatment signal

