17.0 Data Management* and Confidentiality

17.1 Data on four key areas of feasibility will be analyzed using descriptive statistics, including measures of frequency, central tendency, dispersion and variation. See Table above.

17.2 Study staff will complete and stay current on all training regarding data security and confidentiality. Written and electronic data will be coded by subject number. All written data will be kept in study binders or folders in a locked cabinet in the PI's locked office. Electronic data containing any identifiable information (PHI, PII), including audio and video recordings, will be kept in a VA protected environment (e.g., VA-approved servers). Audio and video recordings obtained on VA-approved devices will be transferred to a VA-approved server using a VA-issued USB device.

17.3 Checklists will be used to ensure that all study procedures are completed. Reliability checks will be completed on data from assessments.

17.4 Describe how data or specimens will be handled study-wide: All data will be stored on the VA trusted server. Data will be stored in closed systems with access only for study team members on VA trusted server. Identifiable data will only be stored for the length of the study plus any unanticipated delay time. If data is retained after this time it will be de-identified. Study team members will have access to the data. The PI is ultimately responsible for the receipt of the data and storage to the appropriate locations. Data will not be transported as it will be stored to the appropriate online storage from its collection point.

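### Aim 3 is to be judged by raw percent agreement alone, which hides whether the radiology-report rule over-calls or misses frontal lesions

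*Combined protocol and SAP*

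**What the plan says.** The secondary objective in the Study Summary (1.0) is "To demonstrate the feasibility of using information about lesion location from the radiology report to classify frontal vs. nonfrontal lesions". The Aim 3 hypothesis in 2.2 is that the two sets of classifications "are consistent, confirming this adaptation provides a clinically accessible, reliable way to identify brain-based predictors of optimal PAT response".

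Two binary labels are planned per participant (4.1 and the SAP, Adaptation). One comes from brain mapping by trained raters followed by a blinded neurologist's call. The other is a word rule: "Using radiology reports, lesions will be classified as “frontal” based on use of that word or “anterior” “premotor” “prefrontal” or “precentral", and nonfrontal if none of the listed words appears. No handling of negation or context is stated.

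The only analysis named for comparing the labels, in Table 1 of the protocol and again in the SAP table, is "Percent agreement on presence or absence of frontal lesion between radiology report and brain mapping". The general statement in 17.1, repeated at the start of the SAP, is "Data on four key areas of feasibility will be analyzed using descriptive statistics, including measures of frequency, central tendency, dispersion and variation". That would allow a cross-tabulation but does not commit to one. The plan gives no interval, no level of agreement that would count as consistent, and no expected frontal share.

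**The concern.** The label is meant for use. Section 3.1 says that, before selection guidelines are broadly implemented, it must be established that taking lesion location from the report, "as compared to research-based brain mapping methods, is a feasible and reliable method of categorizing lesions". The same section says that developing PAT for large-scale studies in left and right brain stroke "first requires determining whether stratifying patients by frontal lobe lesions reveals differences in treatment benefit". Preliminary Study 4 in 3.2 asks whether the medical record offers a "reliable way to identify patients with frontal vs. nonfrontal lesions".

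For those purposes the direction of error matters. False-frontal calls dilute the report-frontal group with nonfrontal patients. Missed-frontal calls leave frontal patients in the report-nonfrontal group. Someone planning a stratified study would need to know which occurs, and a reader given only percent agreement cannot work it out.

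One-sided error is possible by construction. As written, a report stating that there is no frontal lesion, or using *anterior* of a nonfrontal structure, would be labelled frontal. Whether this happens often is unknown, and the named statistic would not show it.

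**Working it through.** **Inputs.** The target n = 30 is from 1.0 and 12.1. The plan states no expected agreement, precision or frontal share for Aim 3, so it has no figure to reproduce. The 80% agreement and the frontal counts below are assumptions for illustration.

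**Notation.** Against mapping, let a = both frontal, b = report-only frontal (false-frontal), c = mapping-only frontal (missed-frontal), d = both nonfrontal, with n = a + b + c + d.

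- Agreement = (a + d)/n = 1 − (b + c)/n. Only the sum b + c enters, so the split between b and c is lost whenever both lesion classes are present.
- Sensitivity (Se) = a/(a + c); specificity (Sp) = d/(b + d).
- Kappa = (Po − Pe)/(1 − Pe), where Po is the agreement and Pe = [(a + b)(a + c) + (c + d)(b + d)]/n².

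**Step 1: one agreement figure, different error patterns.** Every row has a + d = 24, so agreement is 24/30 = 80%, exact (Clopper–Pearson) 95% CI 61–92%.

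| Frontal by mapping | a/b/c/d | Se | Sp | Nonfrontal among report-frontal | Frontal among report-nonfrontal | Kappa |
|---|---|---|---|---|---|---|
| 15 | 12/3/3/12 | 12/15 | 12/15 | 3/15 (20%) | 3/15 (20%) | 0.60 |
| 15 | 15/6/0/9 | 15/15 | 9/15 | 6/21 (29%) | 0/9 | 0.60 |
| 15 | 9/0/6/15 | 9/15 | 15/15 | 0/9 | 6/21 (29%) | 0.60 |
| 21 | 21/6/0/3 | 21/21 | 3/9 | 6/27 (22%) | 0/3 | 0.41 |
| 21 | 18/3/3/6 | 18/21 | 6/9 | 3/21 (14%) | 3/9 (33%) | 0.52 |
| 21 | 15/0/6/9 | 15/21 | 9/9 | 0/15 | 6/15 (40%) | 0.60 |
| 24 | 24/6/0/0 | 24/24 | 0/6 | 6/30 (20%) | none | 0 |
| 6 | 0/0/6/24 | 0/6 | 24/24 | none | 6/30 (20%) | 0 |

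The last two rows are rules that give every report the same label. Kappa check for 24/6/0/0: Pe = (30×24 + 0×6)/900 = 0.80, so kappa = (0.80 − 0.80)/0.20 = 0.

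The first three rows show that kappa does not recover direction either. Pe is 0.50 in each, so kappa = 0.30/0.50 = 0.60.

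**Step 2: dependence on the lesion mix.** With p the frontal share by mapping, agreement = Se·p + Sp·(1 − p).

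- Se 0.9, Sp 0.5: p = 0.3 gives 0.27 + 0.35 = 0.62; p = 0.5 gives 0.70; p = 0.7 gives 0.78.
- Se = Sp = 0.8: 0.80 at every p.

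The mix therefore moves the figure only when sensitivity and specificity differ. The merging of error types in Step 1 does not need an uneven mix; it is there at 15 and 15.

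**The case against.** The strongest reply is that Table 1 asks only whether the two classifications are consistent, and percent agreement answers that directly. No threshold or test is attached, so no formal conclusion can be wrong. Both labels are recorded for each participant, and a cross-tabulation is a frequency display, so it could be produced later under the general descriptive wording. Nothing in this trial turns on the label: groups are pre-assigned by computer (6.1), and no planned outcome analysis uses frontal status. The illustrative tables are assumed, and the one-label cases are extremes. Finally, sensitivity and specificity treat mapping as a reference, although it ends in one neurologist's call with no stated error rate.

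Much of this stands, and it keeps the point minor. It does not remove it. The 2×2 table can be recovered by the study team, but nothing commits them to report it, and the hypothesis in 2.2 would read consistency as confirming reliability. Section 3.1 itself makes mapping the comparator, so rates taken against it fit the plan's purpose. They should be read as agreement with mapping within each mapped class, without assuming that mapping is free of error.

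**Conclusion.** The concern holds, as a minor point. Percent agreement is the only statistic specified for Aim 3. It conceals the direction of error when both lesion classes are present, and it can score an uninformative rule at 80% when 24 or 6 of 30 lesions are frontal. At an even split, 80% agreement is compatible with sensitivity anywhere from 60% to 100%, with specificity running the opposite way.

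The algebra needs no assumptions. The sizes rest on n = 30, an assumed 24/30 agreement and assumed frontal counts. The practical consequence is limited because Aim 3 is secondary and descriptive, and because the better response in frontal patients has been reported only after right brain stroke (3.1, 3.2).

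**What to change.** In 4.1, Table 1 and the SAP, replace the single statistic with wording such as:

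> *Report classification will be compared with brain mapping by the 2×2 table, percent agreement, and sensitivity and specificity against brain mapping, each proportion with an exact 95% CI.*

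Keep the stated word rule as the primary index method. List the discordant cases with the report wording that produced each call, so that any effect of negated mentions, or of *anterior* used of a nonfrontal structure, is described as a result. Kappa is optional. If it is given, say that it depends on the frontal share and does not show error direction.

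**Cost.** A wording change, one table and a short case list, from two classifications already planned. No new data and no second classification are needed. The intervals will be wide: 12/15 has an exact 95% CI of 52–96%, 6/9 of 30–93% and 3/9 of 7–70%. If mapping puts no one in a class, the corresponding rate cannot be estimated. The results will describe how the rule behaves; they will not settle its reliability.

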4.2 N/A

5.0 Study Intervention/Investigational Agent

5.1 PAT will be administered 5 days per week for 2 weeks (10 sessions) using a portable kit with manual (KF-PAT®; Chen 2015) by a trained study clinician. This spatial retraining approach involves repeated arm movements to visual targets while wearing goggles that shift the visual field horizontally. To treat right-sided neglect, yoked, 20-diopter, right-based wedge lenses (in which the right side is thicker) are used. The prismatic distortion causes the visual illusion that objects in the environment are displaced to the left. Thus, reaching movements with the prisms on are shifted to the left of a fixed target. Over repeated attempts to interact manually with the target through visual-motor practice, spatial processing leads to motor adaptation, and the participant correctly reaches for the target. After removing the prisms, visual information returns to normal, but the spatial-motor system has increased its propensity to move rightward (Fortis et al., 2011). Thus, when the goggles are removed, the participant will reach for a fixed target and miss by making a movement that is directed too far rightward. The Nausea Profile, found on page 15 of the treatment manual, will be administered the first three days of treatment per recommendations.

5.2 N/A

[figure not shown]
5.3 N/A

6.0 Procedures Involved*

6.1 This 7-week prospective study uses a multiple baseline, delayed treatment approach to address four key areas of focus for feasibility studies (Bowen et al., 2009). Participants will be assigned to one of two groups using

computer-generated pre-assignment. Group 1 will begin PAT after two baseline sessions. Group 2 will begin PAT after four baseline sessions.

6.2 Participants will undergo baseline memory and language assessments, along with weekly assessments of functional ability, spatial and motor function, and pain from baseline through 7 weeks. Treatment will be provided 5 days per week for two weeks following a two- or four-week baseline. Assessment and treatment procedures may be conducted face-to-face or by VA-approved audio (phone) or video communication to decrease the amount of face-to-face interaction at the Atlanta VA. Assessment and treatment procedures may be audio and/or video recorded for research purposes. The recordings will be acquired on VA-approved devices. The patients will be informed of the audio or video recording. The recordings will be stored on VA approved servers.

6.3 Risks and procedures to minimize risks are outlined in section 15.0. The source records that will be used to collect data are provided in the IRB smart form and include: Visual Analog Mood Scales (Arruda et al. 1999), the McGill Pain Questionnaire (Melzack 1987), the Michigan Body Map (Brummett et al. 2016), Trail Making Test (Delis, Kaplan & Kramer, 2001), Functional Independence Measure (FIM; Granger et al. 1993) or telephone-administered (FONE-FIM; Chang, Slaughter, et al. 1997; Chang, Chan, et al. 1997), Western Aphasia Battery (Kertesz, 1982), Brief Visuospatial Memory Test- Revised (Benedict et al. 1996), Hopkins Verbal Learning Test- Revised (Benedict et al. 1998), and digit span forward and backward (Lezak et al., 2004), as well as the CSQ-8, CEQ, KF-NAP®, WMFT (described above in section 4.0) and Nausea Profile.

6.4 Data will be obtained through the medical record, assessments of language, memory, spatial, and physical function, pain, and functional ability as described above.

